**Table 4 - Study schedule of events (Part B) for patients with home infusions after Day 273**

Study Visit (Week/Day)	Part B post Day 273 Open-Label Extension Phase	Part B post Day 273 Open-Label Extension Phase m	ET/EOS/Safety Follow-up a
	On site visit	Home visit	9 Weeks after Last Dose On site visit
Visit Windows	± 2 days	± 2 days	± 2 days
Pregnancy test (if applicable) b	X		X
Body weight	X n		X
Physical examination, full			X
Physical examination, brief	X n		
Vital signs (BP, PR, RR, body temperature) c	X n		X
SLE panel d	X d		X

Study Visit (Week/Day)	Part B post Day 273 Open-Label Extension Phase	Part B post Day 273 Open-Label Extension Phase m	ET/EOS/Safety Follow-up a
	On site visit	Home visit	9 Weeks after Last Dose On site visit
Visit Windows	± 2 days	± 2 days	± 2 days
Hematology panel d	X		X
Coagulation panel d			X
Clinical chemistry panel d	X		X
Urinalysis d	X h		X
FACIT-Fatigue j	X h		X
PGIS j	X h		X
PGIC j	X h		X
SF-12 j	X h		X
EQ-5D-5L j	X h		X
Solicited symptomatic anemia	X	X	X
Study drug administration e	X	X	
ADAs against BIVV009 and neutralizing anti bodies	X k		X
PK Samples f	X h		X
PD Samples d, f	X h		X
Concomitant medications including transfusions	X	X	X
Healthcare resource utilization	X i		X
Adverse events g	X	X n	X
Home infusion satisfaction survey		X l	

ADA = anti-drug antibodies; BP = blood pressure; EOS = End of Study; EQ-5D-5L = five level EuroQol five dimensions questionnaire; ET = Early Termination Visit; FACIT-Fatigue = functional assessment of chronic illness therapy - fatigue; N/A = not applicable; PD = pharmacodynamic; PGIC = Patient's Global Impression of Change; PGIS = Patient's Global Impression of [Fatigue] Severity; PK = pharmacokinetic; PR = pulse rate; QOL = quality of life; RR = respiratory rate; SF-12 = 12-Item Short Form Survey;

- a Patients should return to site 9 weeks after last dose for ET procedures, EOS assessment, or Safety Follow-up procedures upon completion of dosing in the study. If patient experiences a hematological breakthrough event, a PK, PD, and ADA sample should be collected at the time of the event.
- b Females of child-bearing potential only. Serum or urine pregnancy test every 4 weeks (+/- 2 days) during Part B at on-site visit and at ET/EOS safety follow-up visit
- c Vital signs measurements (supine BP, PR, RR, and oral temperature) are to be obtained with measurements performed pre-dose and 1 hour (±5 minutes) after completion of administration of each dose of study drug (on site visits only).
- d For a complete list of analytes, see protocol [Appendix A](#). SLE panel testing should occur every 6 months at on site visits in Part B.
- e Study drug doses of 6.5 grams (if <75 kg) or 7.5 grams (if ≥75 kg) based on patient's baseline body weight will be administered via IV infusion over ~ 60±5 minutes, every 2 weeks during Part B. Patients with underlying cardiopulmonary disease may receive a 2-hour infusion with Sponsor approval. If a patient misses a scheduled dose (outside of the 2-day window or >17 days since last dose), they must return to site (unscheduled visit) to receive another loading dose 1 week prior to the next scheduled dose.

- f During Part B, PK and PD samples will continue to be collected routinely at predose and 1 hour ( $\pm 15$  minutes) postdose at 3-month intervals starting at Day 273 through the remainder of the study. PK and PD samples will also be collected if a patient experiences a hematologic breakthrough event at any point during the study.
- g AEs will be recorded from the time the patient signs the informed consent form until 9 weeks after administration of the last dose of study drug. For patients with home infusions, safety assessments will additionally include AEs with onset within 24 hours of the of infusion.
- h To be performed every 3 months during the on-site visits.
- i During Part B, the healthcare resource utilization data will be recorded every 4 weeks, at on site visit;
- j To be performed in the following order: FACIT-Fatigue first, PGIS second, PGIC third, SF-12 fourth, and EQ-5D-5L fifth.
- k During Part B post Day 273, ADA samples will be collected every 3 months predose, and at Safety Follow up visit 9 weeks after last dose. Samples will also be collected if a patient experiences a hematologic breakthrough event or withdraws from the study early.
- l After the 1st and 4th home infusions
- m Post-Day 273 extension phase home visit is alternating with every 4 weeks with site visit and if needed, a loading dose can be infused at the site visit.
- n HCP records and AEs will be collected on paper forms and will be forwarded to PI within 24h; site will be informed of any AEs immediately; All SAE reporting timelines still apply (ie need to be reported to sponsor safety database within 24 hours of awareness by the home infusion healthcare professional).

## **Section 2.2 (Background and Study Rationale)**

Patients with CAgD are often elderly and/or have numerous co-morbidities affecting their mobility. Moreover, clinical centers specialized in the management of CAgD are infrequent and may be located far from patients' home. Consequently, some patients may find the option of home infusions with drug against CAgD, beneficial. To this end a group of patients at preselected sites/countries will be offered the possibility of home infusions during Part B, assisted by trained health care professional.

### **Section 2.2.4 (Potential Risks and Benefits)**

Home infusions with the study drug will be proposed to a number of patients in countries pre-selected to participate in home infusion. Home infusions will be assisted by a trained healthcare professional, and will concern patients who express such wish, after having been qualified by the Investigator and no sooner than after Week 39 (Day 273) and without evidence of hypersensitivity to study drug. Only patients treated with BIVV009 for the minimum of 3 months and in whom previous infusions with BIVV009 were not associated with a hypersensitivity reaction are eligible for the home infusion. Additionally, patients who are participating in or have ever participated in undiluted infusions are not eligible for home infusions. Rescue medications to treat hypersensitivity/allergic reactions as per the PI's guidance will be immediately available during home infusion visits. The home infusion personnel will be trained in basic life support (cardiopulmonary resuscitation [CPR]) but will not be required to have equipment to perform advanced life support (eg, defibrillators).

### **Section 3.5 (Exploratory objective [Part B])**

- To describe the safety and patient satisfaction with the convenience of home infusions with BIVV009 in a subset of patients in the US, the Netherlands, Norway, France, Italy, Austria, Germany, and Spain.

### **Section 4.1 (Study Design: Part-B)**

A subset of patients from selected sites/countries, who have been treated for a minimum 3 months (completed visit Day 273) in Part B, and who were determined to have tolerated BIVV009 well, will be invited to have infusions with BIVV009 performed at their homes, after

having been qualified by the Investigator. Home infusions will be carried out by a trained nurse. Patients will follow the alternate home infusion scheme, ie, home infusion at the patient's home will be alternating with office visits, so that patients will attend office visit every 4 weeks alternating with home infusions every 4 weeks (+/- 2 days).

### **Section 6.1, Table -3 (Footnote "i")**

Study drug doses of 6.5 grams (if <75 kg) or 7.5 grams (if  $\geq$ 75 kg) based on patient's baseline body weight will be administered via IV infusion over  $\sim 60\pm 5$  minutes on Days 0, 7, and every 14 days thereafter during Part A and every 2 weeks starting at Week 27 during Part B. Patients with underlying cardiopulmonary disease may receive a 2-hour infusion with Sponsor approval. If a patient misses a scheduled dose (outside of the 2-day window or >17 days since last dose), they must return to site (unscheduled visit) to receive another loading dose 1 week prior to the next scheduled dose. Qualifying patients at participating sites may have study drug dosed at home, alternating with study drug dosed during office visits in Part B.

### **Section 6.1.5.5 (Infusion of the study drug at patient's home)**

Home infusions will be performed at pre-selected countries/sites by a healthcare professional caregiver contingent upon completion of training delivered by the Investigator or delegated site staff member only in patients willing to be administered study drug at home, who have been treated for at least 3 months (completed visit Day 273) with the study drug BIVV009 in Part B, and in whom previous on-site infusions were uncomplicated, who satisfy the following criteria:

1. Able to comprehend and give informed consent for participation in the alternate home infusion scheme and willing to be infused at home for at least 4 doses, alternating with regular office visits.
2. Treated for at least 3 months in Part B (completed visit Day 273)
3. No history of hypersensitivity reaction to BIVV009
4. Considered by the investigator to be a good candidate for home infusions
5. Not participating in, or have never participated in undiluted infusion administration

Qualifying patients who consent for home infusions will have study drug administered in home every other bi-weekly visit alternating with regular office visit with drug infusion. Qualification for home infusions and informed consent will be collected no later than at office visit two weeks before first planned home infusion.

For subjects receiving drug injections in home as administered by a healthcare professional during the Part B open-label phase, the healthcare professional will collect specific information (AEs, concomitant medications, solicited anemia assessment as well as, after the 1st and 4th home infusions, the patient will answer the Home Infusion Patient Satisfaction Survey). The data collected on dedicated paper forms will be provided to the Investigator within 24 hours for entry in EDC. The healthcare professional will monitor the subject during 1-hour or, in certain patients 2-hour infusion (eg, patients with underlying cardiopulmonary disease, with sponsor's approval) and for at least 1 hour after the completion of the first home infusion or 2 hours after the

completion of each subsequent home infusion. Any adverse events occurring during home visits will be immediately reported by the healthcare professional caregiver to the Investigator.

First office visit 2 weeks after first home infusion will include assessments normally planned to be performed every 3 months. Neither blood samples nor urine pregnancy tests will be collected/performed during home infusion visits; blood tests scheduled to be performed at 2, or 4 weeks intervals as well urine pregnancy tests in WOCBP (ie, women of child bearing potential) will be performed during office visits every four weeks while the patient is within the home infusion scheme.

In case a scheduled home infusion visit happens to coincide with an every 3 month office visit, rather than this visit occurring at home, the patient should attend the office visit with study drug infused at the office site. The next home infusion visit will then occur 2 weeks later. Subsequently, the bi-weekly alternating office and home visits with drug infusions will then resume as previously planned.

Patients who miss a dose (ie, outside the dosing window or >17 days since last dose, regardless if last dose was given at home or at the site) should return to the site for an unscheduled visit to receive another loading dose prior to their next scheduled visit which will also take place at the office. Such patient may return to the schedule of home visits alternating with regular office visits if eligibility criteria for home infusions are still met.

Patients undergoing home infusions with BIVV009 will return to bi-weekly dosing at the study site if they experience adverse event that in the opinion of the Investigator, may jeopardize patient safety if home infusions are continued. Patients may return to home infusions if this AE is considered by the Investigator to be unrelated to BIVV009 and once resolved or stabilized. Hypersensitivity or allergic reactions to study drug will always result in study drug discontinuation and withdrawal from the study.

Infusions given in the home setting versus at the investigational site will be captured through the case report form (CRF) for drug administration.

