#### **6.1.5.5 Infusion of the study drug at patient's home**

Home infusions will be performed at pre-selected countries/sites by a healthcare professional caregiver contingent upon completion of training delivered by the Investigator or delegated site staff member only in patients willing to be administered study drug at home, who have been treated for at least 3 months (completed visit Day 273) in Part B and in whom previous on-site infusions were uncomplicated (for the US, the Netherlands, Norway, France, Italy, Austria, Germany, and Spain, specific amendments) ([Appendix K](#)). Only patients who do not participate in, or have never participated in undiluted infusions can be considered for home infusion.

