Patients must be monitored for acute allergic reactions during infusion and for at least 2 hours after the completion of the first administration of study drug or 1 hour after the completion of each administration of study drug thereafter. Additionally, patients undergoing home infusions will be monitored by the professional healthcare caregiver for 2 hours after the completion of the first home infusion or 1 hour after the completion of each subsequent home infusion ([Appendix K](#)). Epinephrine, parenteral diphenhydramine and, for infusions carried at the study site, cardiac resuscitation equipment, must be immediately available in case an allergic reaction or anaphylaxis occurs. Site personnel or professional healthcare caregiver in case of home infusions ([Appendix K](#)), must be qualified to detect allergic reactions and anaphylaxis and treat those reactions under the guidance of the PI. The home infusion personnel will be trained in basic life support (cardiopulmonary resuscitation [CPR]) but will not be required to have equipment to perform advanced life support (eg, defibrillators). See [Section 6.3.8](#) for further details regarding additional testing.

Patients should be instructed to report the development of rash, hives, pruritus, flushing, urticaria, etc, that may represent an allergic or hypersensitivity reaction to study drug. If any signs or symptoms of an allergic or anaphylactic reaction are observed during the infusion, administration of study drug must be immediately discontinued and the patient treated as appropriate. In case of home infusion, the investigator has to be notified immediately to guide treatment ([Appendix K](#)).

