### **Synopsis (Test Product(s), Dose, and Mode of Administration)**

Home infusion will be performed at pre-selected countries/sites by a healthcare professional caregiver contingent upon completion of training delivered by the investigator or delegated site staff member only in patients willing to be administered study drug in home, who have been treated for at least 3 months (completed visit Day 273) with the study drug BIVV009 in Part B, in whom previous on-site infusions were uncomplicated, and who satisfy the following criteria:

1. Able to comprehend and give informed consent for participation in the alternate home infusion scheme and willing to be infused at home for at least 4 doses, alternating with regular office visits.
2. Treated for at least 3 months in Part B (completed visit Day 273)
3. No history of hypersensitivity reaction to BIVV009
4. Considered by the investigator to be a good candidate for home infusions
5. Not participating in, or have never participated in undiluted infusion administration

Qualifying patients who consent for home infusions will have study drug administered in home every other bi-weekly visit alternating with regular office visit with drug infusion. Qualification for home infusions and informed consent will be collected no later than at office visit two weeks before first planned home infusion.

For subjects receiving drug injections in home as administered by a healthcare professional during the Part B open-label phase, the healthcare professional will collect during home visits specific information (AEs, concomitant medications, solicited anemia assessment, as well as, after the 1st and 4th home infusions, the patient will answer (by filling up the form) the Home Infusion Patient Satisfaction Survey) ([Appendix L](#)). The data collected on dedicated paper forms will be provided to the Investigator within 24 hours for entry in EDC. The healthcare professional will monitor the subject during infusion lasting 1-hour or, in certain patients 2-hour (eg, patients with underlying cardiopulmonary disease, with sponsor's approval) and for 2 hours after the first home infusion dose and 1 hour after the completion of each subsequent home infusion. Any adverse events occurring during home visits will be immediately reported by the healthcare professional caregiver to the Investigator.

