#### **Section 6.2.4 (Dose Preparation and Administration)**

Patients must be monitored for acute allergic reactions during infusion and for at least 2 hours after the completion of the first administration of study drug at a home infusion visit or 1 hour after the completion of each administration of study drug thereafter at subsequent home infusion visits.

Epinephrine, parenteral diphenhydramine and, for infusions carried at the study site, cardiac resuscitation equipment, must be immediately available in case an allergic reaction or anaphylaxis occurs. Site personnel or professional healthcare caregiver in case of home infusions

([Appendix K](#)), must be qualified to detect allergic reactions and anaphylaxis and treat those reactions under the guidance of the PI. The home infusion personnel will be trained in basic life support (cardiopulmonary resuscitation [CPR]) but will not be required to have equipment to perform advanced life support (eg, defibrillators). See [Section 6.3.8](#) for further details regarding additional testing.

Patients should be instructed to report the development of rash, hives, pruritus, flushing, urticaria, etc, that may represent an allergic or hypersensitivity reaction to study drug. If any signs or symptoms of an allergic or anaphylactic reaction are observed during the infusion, administration of study drug must be immediately discontinued and the patient treated as appropriate. In case of home infusion, the investigator has to be notified immediately to guide treatment.

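### Protocol Appendix K Section 6.1.5.5 swaps the home observation times: 1 hour after the first infusion and 2 hours after later ones, where three other places say 2 hours, then 1

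*Protocol*

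**What the plan says.** Four places in the current protocol state how long a patient is observed after a home infusion.

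- Appendix K, Section 6.1.5.5: "for at least 1 hour after the completion of the first home infusion or 2 hours after the" end of each subsequent one.
- Main protocol, Section 6.2.4: "for 2 hours after the completion of the first home infusion or 1 hour after the completion of each subsequent home infusion".
- Appendix K, Synopsis: "for 2 hours after the first home infusion dose and 1 hour after the completion of each subsequent home infusion".
- Appendix K, Section 6.2.4: "for at least 2 hours after the completion of the first administration of study drug at a home infusion visit or 1 hour" after later ones.

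The general rule in main Section 6.2.4, which covers every infusion wherever it is given, asks for at least 2 hours after the first administration of study drug and "1 hour after the completion of each administration of study drug thereafter".

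Main Section 6.1.5.5 gives no observation time. It restricts home infusion to patients treated for at least 3 months "in Part B and in whom previous on-site infusions were uncomplicated" and refers to Appendix K. Table 4, the schedule for home-infusion patients, gives no observation time either.

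**The concern.** The observation period exists to catch acute allergic reactions. One section of Appendix K gives the shorter period to the first home infusion, and every other statement gives it the longer one. The caregiver is away from the site, and Section 6.2.4 does not require advanced life support equipment in the home. Table 4 footnote c schedules vital signs 1 hour "after completion of administration of each dose of study drug (on site visits only"), so at home the caregiver's own observation is the main post-infusion check.

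Two things are at stake. A caregiver working from Section 6.1.5.5 could leave before the other three places allow. A monitor also has no single standard for judging compliance at any home visit, because the later infusions conflict as well, in the other direction.

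**Working it through.** No formula in the plan bears on this point, so the check is a comparison of texts followed by some simple counts.

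**Side by side**

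| Place | First home infusion | Each later home infusion |
|---|---|---|
| Appendix K, Section 6.1.5.5 | at least 1 h | 2 h |
| Main protocol, Section 6.2.4 | 2 h | 1 h |
| Appendix K, Synopsis | 2 h | 1 h |
| Appendix K, Section 6.2.4 | at least 2 h | 1 h |

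Three places agree and one differs.

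**Which text is wrong.** A deliberate country-specific rule would explain a difference between Appendix K and the main text. It cannot explain a difference within Appendix K, and two of the three agreeing places are in that appendix. The general infusion rule also puts the longer period first. The documents give no reason to observe later home infusions longer than the first. The sentence is complete and is current text, not amendment history. That Section 6.1.5.5 is the slip is an inference, but a strong one.

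**Size of the shortfall**

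- First home infusion: 2 h − 1 h = 1 h at most, because the 1 h is worded as a minimum. It arises once per patient.
- Later home infusions: Section 6.1.5.5 asks for 2 h − 1 h = 1 h more than the other places, so these are not under-observed.
- Over the four home doses a patient agrees to: 1 + 2 + 2 + 2 = 7 h under Section 6.1.5.5, against 2 + 1 + 1 + 1 = 5 h under the others.

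**Earlier exposure.** Inputs: biweekly Part B dosing from Week 27, which is Day 189 (protocol Section 4.1 and the sampling days in Section 4.3.6); home infusion only after the Day 273 visit (Appendix K); and 14 protocol-specified Part A doses (Part A SAP Section 4.7.1).

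- Part B doses through Day 273: (273 − 189)/14 + 1 = 7.
- Randomized to placebo: 7 + 1 BIVV009 loading dose at Week 26 = 8.
- Randomized to BIVV009: 7 + 14 = 21. Their Week 26 crossover dose is placebo and is not counted.

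These are minimums if no dose is missed, since home infusion may start later than the first visit after Day 273.

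**Patients affected.** The documents give no number. Of about 40 randomized patients, at least 15 are to receive undiluted infusions and are then barred from home infusion, which leaves at most about 40 − 15 = 25. If no patient received undiluted infusions, the ceiling would be about 40. Both figures assume that every randomized patient enters Part B. Both are loose, because only pre-selected sites in eight countries offer home infusion.

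**The case against.** The strongest reply is that this is a typographical slip with little consequence. Much of that stands.

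- A caregiver who stays 2 hours after the first infusion satisfies all four places. Only someone who reads Section 6.1.5.5 alone and stops at its minimum under-observes.
- Appendix K opens with its synopsis, so a reader who starts at the beginning meets the 2-then-1 rule first.
- One hour is already the protocol's standard for every dose after a patient's first. These patients have no hypersensitivity history and had uncomplicated on-site infusions.
- Rescue medication "will be immediately available during home infusion visits", and caregivers must complete training by the investigator or a delegate. That training may state the right times, though the documents do not show it.
- The vital-signs contrast is weaker than it looks. Protocol Section 6.1.5.3 and Table 3 footnote l put Part B vital signs at three-monthly visits, and the two-weekly list in Section 6.1.5.1 omits them. Table 3 footnote g is broader, but under the schedule most diluted on-site Part B infusions have no post-dose vital signs either.

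None of this makes the four statements agree. The reply limits the risk. It does not give a reading in which Section 6.1.5.5 is right.

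**Conclusion.** The concern holds. Appendix K Section 6.1.5.5 is wrong as written. Its practical effect is up to 1 hour less observation at one visit per patient, in a group that cannot exceed about 25 to 40 and is probably smaller. Absolute risk is low, and sample size, power, endpoints and analyses are unaffected. The point should still be corrected, because it is an operative safety instruction for staff working away from the site. The conclusion rests on one inference: that the three agreeing places, and not the single outlier, state the intended times.

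**What to change.** In Appendix K Section 6.1.5.5, set the observation period to at least 2 hours after the end of the first home infusion and 1 hour after the end of each later one. Send a short letter to sites and home-infusion providers now, and check that caregiver training materials carry the same times.

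The cost is one sentence at the next amendment plus the letter. Data collection and analysis do not change.
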